4.3 JUSTIFICATION FOR INTERVENTION

The CBT intervention will consist of up to 12 weekly 60 minute sessions of the manualized therapy, adapted from the Coping Cat program, for the treatment of pediatric anxiety disorders. The CBT+CCT intervention will consist of ~30 minutes of CCT games prior to each CBT session, to engage cognitive control capacity prior to receipt of CBT. They may also receive up to 4 weeks of at home CCT to complete for up to two weeks before starting CBT and up to 4 weeks after starting CBT (~30 minutes per session). If assigned, this may be done at home 5 days per week. The CCT games will be designed to target focused attention, response inhibition, working memory and multiple simultaneous attention to constitute a general executive function training, and activate neural systems associated with executive function/cognitive control. Difficulty of the games will be titrated individually and by session to avoid boredom and progressively activate the functional systems underlying cognitive control, which we hypothesize will optimize participant's ability to engage in, and thus benefit from, in the CBT intervention. For both groups, participants will have to complete at least 8 intervention sessions.

4.4 END-OF-STUDY DEFINITION

A participant is considered to have completed the study if he or she has completed the baseline assessment, at least 8 intervention sessions of CBT (for CBT group) or CCT+CBT (for CBT+CCT group), pre and post fMRI scans, NIH toolbox and/or Millisecond assessments, and final independent evaluation. At P.I. discretion, participants may be considered to have completed the study even if they have not completed all of these activities.

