1.3 SCHEDULE OF ACTIVITIES

The following assessments and study activities may be done at each time point. For NIH Toolbox and PARS assessments, some variability in administration may occur based on subject's schedule. All assessments completed as part of [name] study *Dimensional Brain Behavior Predictors of CBT Outcomes in Pediatric Anxiety (HUM00118950)* will not be repeated for this protocol and previously collected data will be used. At P.I. discretion, participants may also not be required to complete an fMRI.

CBT-Only Timeline of Events (Primary Arm, [name] HUM00118950)

CBT+CCT Timeline of Events (Primary Arm, [name] HUM00169730)

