4 STUDY DESIGN

4.1 OVERALL DESIGN

We hypothesized that computerized cognitive training (CCT), through engaging the task-control network and increasing cognitive control capacity, may augment the CBT response. In this study, eighteen clinically anxious children ages 7 to 17 will be recruited and assigned to CBT+CCT for up to 12 weeks; thirty-six age- and gender-matched anxious children will be recruited and assigned to CBT only for up to 12 weeks. Before and after therapy, all participants may complete structured clinical assessment of anxiety, a computerized evaluation of cognitive control capacity (e.g., NIH Toolbox; Zelazo, Anderson, Richler, Wallner-Allen, and Beaumont, 2013) and MRI scanning during a cognitive interference task and resting-state to assess brain activation and functional connectivity in the TCN. However, at P.I. discretion, participants may not be required to complete an fMRI. Participants may also complete structured clinical assessment of anxiety, computerized evaluation of cognitive control capacity, and MRI scanning during therapy.

This study will be incorporated into an ongoing fMRI study (HUM00118950, PI [name]) investigating dimensional brain-behavioral predictors of CBT outcomes in pediatric anxiety. In the parent R01 (HUM00118950), 210 youths (7-17 years) with impairing anxiety are being recruited and randomized 2:1 to receive 12-week CBT or a non-active control therapy, “relaxation and mentorship therapy” (RMT);

multilevel data including fMRI, DTI and clinical measures are collected before and after treatment. As part of the parent study, RMT completers are offered study CBT (at no cost), without additional scanning.

Study activities that may be completed remotely (i.e., Millisecond behavioral assessment, clinical measures and assessments, CCT, and CBT through the parent study) will be conducted via an encrypted HIPAA-compliant video conferencing platform (e.g., BlueJeans, Zoom), phone call, and/or Millisecond/Qualtrics links. It will be standard practice to conduct as many procedures remotely as possible to better protect subject(s)/parent(s) and staff against the risk of COVID-19. However, when remote visits are not possible (e.g., NIH toolbox behavioral assessments, fMRI), in-person visits will be allowed and the study will follow all U-M safety guidelines for entering and being in U-M buildings (e.g., COVID screenings, PPE, social distancing, etc.).

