6.3 MEASURES TO MINIMIZE BIAS: RANDOMIZATION AND BLINDING

There is no randomization in this pilot study. Participants are recruited from the parent study where assignment to the two treatment arms (CBT vs RMT) is stratified based on age and gender, using block randomization to ensure a 2:1 ratio of participants in CBT vs. RMT group (HUM00118950). In this study, we will recruit all possible participants in the RMT group in the parent study to participate in CBT+CCT, and recruit age- and gender-matched participants from CBT group. Efforts will be made to keep therapists blinded to participant group (i.e., CBT+CCT vs. OPT CBT).

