8.1.3 FMRI SCANS

Staff and subjects/parents will follow the fMRI Lab COVID-19 safety guidelines at all times.

Overview: fMRI scans will be performed at two time points for the parent protocol – after the initial assessment and prior to the onset of the first course of treatment (~0 - 14 days prior for anxious participants), and after the completion of treatment (~0 - 30 days after the last therapy session. For the current protocol, an additional scan may be performed following completion of the 4 weeks of at home CCT and at the end of CBT+CCT. If more than about 6 weeks have elapsed since their second scan through the parent protocol, a repeat scan may be obtained prior to the onset of CBT+CCT. Immediately prior to the fMRI session, we will review the MRI protocol, repeat screening for contra-indications to MRI and have subjects remove all objects from their person that could be disturbed by the magnetic fields. They will then undergo the fMRI session (approximately 1-1.5 hours for setup and acquisition). The fMRI methods described below will be the same for each of the scans participants will undergo. Should a participant wish to receive an image of their brain, one will be provided. Please note that, at P.I. discretion, participants may not be required to complete an fMRI.

Assessments prior to each fMRI scan:

- 1) Review of fMRI safety form (copy to fMRI lab)
- 2) Urine pregnancy test for women who endorse possibility of pregnancy.

Placement in the Scanner:

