9 STATISTICAL CONSIDERATIONS

9.1 STATISTICAL HYPOTHESES

- Primary Endpoint(s): Change in Brain activation and connectivity in the task-control network (TCN)

We hypothesize that **(a)** both groups will have increased activation and functional connectivity in task-control network after therapy vs. before therapy; however, **(b)** the increase will be greater in CBT+CCT vs. CBT only group. Baseline and week 12 assessment will evaluate pre- to post-CBT changes in brain activation and function connectivity in the task-control network including fronto-parietal and cingulo-opercular regions mediating cognitive control. Functional activation and connectivity of these brain regions are assessed using a conflict interference computer task performed during MRI scanning.

- Secondary Endpoint(s):
 - (1) Change in behavioral performance on the conflict interference task and tasks testing cognitive control capacity included in the NIH Toolbox: We hypothesize that **(a)** both groups will have improved behavioral performance on the conflict interference task and tasks testing cognitive control capacity included in the NIH Toolbox; however, **(b)** these effects will be greater in CBT+CCT vs. CBT group. This will be evaluated using two measures of the same construct at baseline and week 12. Pre- to post-CBT changes in the behavioral performance in a conflict interference task will be collected, as well as composite score from tasks included in the NIH toolbox.
 - (2) Change in Pediatric Anxiety Rating Score (PARS): We hypothesize that relative to CBT group, anxiety severity will be reduced more and treatment response rate will be higher in CBT+CCT group. This will be evaluated at baseline and week 12 through the PARS, a 50 question interview-based tool used to assess for the presence and severity of anxiety symptoms in children and adolescents utilizing parental and youth input to guide clinician ratings. The total scores on this scale range from 0 to 30, with scores above 13 indicating clinically meaningful anxiety.

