9.3.2 ANALYSIS OF THE PRIMARY ENDPOINT(S)

We hypothesize that CCT will further increase TCN activation and connectivity. The hypothesis will be tested using 2 (within-subject: pre vs. post) x 2 (between-subject: CBT vs. CBT+CCT) repeated-measures ANOVAs on brain activation and connectivity in TCN.

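### The P.I. may excuse participants, without criteria, from the fMRI that alone supplies the primary endpoint, so nothing prevents outcome-related selection into the primary comparison

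*Combined protocol and SAP*

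**What the plan says.** Sections 1.1, 3 and 9.1 name TCN activation and connectivity as the primary endpoint, and Section 9.1 frames it as change from baseline to week 12. Section 9.3.2 tests it with pre/post by group "repeated-measures ANOVAs on brain activation and connectivity in TCN".

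Three sections make the scan optional. Section 4.1 provides that "at P.I. discretion, participants may not be required to complete an fMRI". The schedule in Section 1.3 says "At P.I. discretion, participants may also not be required to complete an fMRI", and Section 8.1.3 repeats the permission alongside the scanning procedures. None of them gives grounds for a waiver, a time by which it must be decided, a reason to be recorded, or a decision-maker blind to group or outcome.

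Section 4.4 lists both scans among the requirements for completing the study and then relaxes the whole list: "At P.I. discretion, participants may be considered to have completed the study even if they have not completed all of these activities".

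On allocation, Section 6.3 states: "There is no randomization in this pilot study". Blinding is described for the evaluator (Section 6.2.1) and, as an effort, for therapists (Section 6.3). Nothing is said about the P.I. Section 4.1 lists the scans after at-home CCT and after CBT+CCT as additions made by this protocol for the CBT+CCT group. The CBT-only scans come from the parent study. Section 9 defines no analysis set and no handling of missing scans.

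**The concern.** A pre-to-post change exists only for someone scanned twice, and a repeated-measures ANOVA in its standard form drops anyone with one scan missing. The person who excuses a scan therefore decides who contributes to the primary comparison.

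For the scan after CBT+CCT, that decision concerns a participant whose group is evident from the scan itself. It falls at the end of treatment, when clinical course is known. Investigators meet weekly to monitor the study (Section 10.1.6), and the P.I. takes part in judging adverse events (Section 8.3.5).

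The plan's own fourth aim (Section 4.2) predicts that TCN increases go with better treatment outcome. If so, a waiver related to clinical course selects indirectly on the primary endpoint. Section 9.2 says that the pilot's product is effect sizes for a later grant application, so a biased estimate does harm whether or not any test is significant.

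**Working it through.** **1. The plan's own count.** Section 5 gives 36 CBT and 18 CBT+CCT participants, therapy retention of 96.2% and a motion rate of 89%. It expects 32 and 14 with usable pre and post data.

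- CBT: 36 × 0.962 × 0.89 = 30.8 (stated 32)
- CBT+CCT: 18 × 0.962 × 0.89 = 15.4 (stated 14)
- Total: 46.2 (stated 46)

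The total reproduces, and each group is within 2. The stated basis is therapy retention and motion only, with no allowance for waived scans.

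**2. Which rule controls entry to the primary comparison.**

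| Rule | Section | Effect on the primary analysis |
|---|---|---|
| Scan may be waived | 1.3, 4.1, 8.1.3 | Direct: no scan, no change score |
| Completion may be declared | 4.4 | None stated: Section 9 does not use completion status |

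The scan waiver is therefore the operative rule, and the completion clause is secondary.

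**3. How far selection could move the estimate.** Section 9.2 gives no SD, effect size or power, so this is an illustration under assumptions that are not in the documents:

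- there is no true group difference;
- there is one standardised TCN change score;
- the 32 CBT participants are unselected;
- the *k* of 18 CBT+CCT participants with the worst clinical change are excused;
- clinical change and TCN change correlate at ρ.

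The expected shift is ρ × m(k), where m(k) is the mean of the top 18 − k of 18 standard normal values. By simulation (200,000 draws), m(2) = 0.198 and m(4) = 0.363. For example, 0.5 × 0.363 = 0.18. A direct simulation of the two-group comparison (20,000 replicates per cell) gives:

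| ρ | Shift, 2 excused | Shift, 4 excused | Two-sided 5% test rejects (2 / 4 excused) |
|---|---|---|---|
| 0 | 0.00 SD | 0.00 SD | 4.7% / 5.0% |
| 0.3 | 0.06 SD | 0.11 SD | 5.4% / 6.5% |
| 0.5 | 0.10 SD | 0.18 SD | 6.4% / 8.4% |
| 0.7 | 0.14 SD | 0.26 SD | 7.5% / 12.6% |
| 1 (upper bound) | 0.20 SD | 0.36 SD | not run |

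The shift favours CBT+CCT here because the worst are excused. Excusing those who do best would reverse the sign.

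**4. Scale.** The difference detectable with 80% power at two-sided 5%, using the stated 32 and 14, is (1.960 + 0.842) × √(1/32 + 1/14) = 2.802 × 0.3204 = 0.90 SD. The largest shift at ρ = 0.7 is 0.26/0.90 = 29% of that. The upper bound is 0.36/0.90 = 40%.

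**The case against.** **The motives were logistical.** The amendment history ties the waiver to social distancing (version 4.0) and the completion clause to funding that ended on 07/31/2021 while study activities take 12 to 28 weeks (version 7.0). These are reasonable motives, but the current text is not confined to them. Section 4.1 already allows in-person fMRI under pandemic safety rules and grants the discretion separately.

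**Other provisions push the other way.** Section 7.1 keeps outcome assessments on schedule, if possible, after treatment is stopped, and Section 9.3.4 lists all measures by time point, so an absent scan would show. Both help, but neither records why a scan was waived. Section 8.2 makes missed PARS and safety assessments reportable deviations. Other missed assessments count only above 10% of the total, and a waived scan appears to fall there.

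**Stronger readings that the documents do not support.** A reader might infer any of the following:

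- *The completion clause removes people from the primary analysis.* It defines no analysis set.
- *The P.I. is stated to know the group.* This is an inference from the lack of randomization, the absence of any stated P.I. blinding and the group-specific scans.
- *Either scan of any participant can be waived under this protocol.* The version 4.0 log entry mentions pre- and/or post-CBT scans, but the current text does not say which scans it covers. Whether it can excuse a parent-protocol scan cannot be judged from these documents. Its clear reach is the added CBT+CCT scans.
- *The bias is 0.20–0.36 SD.* That needs selection directly on TCN change, which nobody can see when the post scan has not been done.

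**Which endpoint is primary.** Sections 4.1 and 8.2 call clinician-rated anxiety the primary outcome, against Sections 1.1, 3 and 9.1. These need reconciling. The point here concerns the TCN endpoint.

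**Conclusion.** The point holds as a gap in the safeguards. The plan states a rule under which the person running the study may decide, without criteria and with group and clinical course visible, who supplies primary-endpoint data. Nothing shows that waivers will depend on outcome, and nothing prevents it.

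Under the assumptions in the working, the plausible distortion from excusing 2 to 4 of 18 is about 0.06 to 0.26 SD for correlations of 0.3 to 0.7, and nil if clinical and TCN change are unrelated. A reader might conclude that a few waivers could create or remove an effect. The figures do not support that: even the upper bound is well below the 0.90 SD detectable difference. The secure claim is that the effect-size estimate could be materially biased, which bears directly on the pilot's stated purpose. The change should be made, but no figure in the plan is wrong because of this point.

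**What to change.** **Protocol text.** In Sections 1.3, 4.1 and 8.1.3, and in Section 4.4 for consistency, replace the open discretion with listed logistical or safety reasons: MRI contraindication, facility closure, end of funding. Require the reason to be dated before any post-treatment outcome is seen. Log participant refusal and inability to tolerate the scanner as separate categories. Both are legitimate reasons for a missing scan, but a child who is doing badly may be more likely to refuse, so they should not be treated as unrelated to outcome.

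**Analysis.** In Section 9.3.2, fit a mixed model to the pre and post scans, including everyone who started treatment and has at least one usable scan. Leave the mid-treatment scan out of this contrast, because only the CBT+CCT group has it. State that the model assumes missing-at-random. It does not remove bias from selection on unseen post values, so it complements the closed list and does not replace it. Report waived and missing scans by group and reason.

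**Cost.** A short protocol edit, one extra log field and a routine model. The downside is less freedom to excuse a scan for other reasons.

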5 STUDY POPULATION

Fifty-four clinically anxious youth will be studied (36 CBT, 18 CBT+CCT). All subjects will be between 7 and 17.99 years old at the time of initial consent. Subjects will be recruited from an existing R01 study at the University of Michigan (HUM00118950, PI [name]), also referred to as parent study. The R01 parent study, at year 4 of the five-year period, has successfully recruited and retained over 100 anxious youth with moderate or greater levels of symptoms, e.g., PARS score > 10 and CGAS score < 60; it will recruit over 100 additional anxious youth randomized 2:1 to CBT and RMT through 05/31/2021. To date, nearly all participants randomized to RMT in the parent R01 study have chosen to continue the CBT sessions after RMT completion; thus we expect 44 youth to be eligible for the CBT+CCT, providing ample opportunity to recruit 36 CBT and 18 CBT+CCT over the one year period of the proposed study. Based on the retention rates of therapy (96.2%) and fMRI motion (89%) in the parent R01, we expect to have 32 CBT-treated and 14 CBT+CCT-treated anxiety youth with usable pre- and post-treatment data.

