7.2 PARTICIPANT DISCONTINUATION/WITHDRAWAL FROM THE STUDY

Participants are free to withdraw from participation in the study at any time upon request.

An investigator may discontinue a participant from the study for the following reasons:

- Significant study intervention non-compliance, i.e. inability or unwillingness to complete study intervention or outcome assessments
- Lost-to-follow up; unable to contact subject (see **Section 7.3, Lost to Follow-Up**)
- Any event or medical condition or situation occurs such that continued collection of follow-up study data would not be in the best interest of the participant or might require an additional treatment that would confound the interpretation of the study
- The participant meets an exclusion criterion (either newly developed or not previously recognized) that precludes further study participation
- The study is suspended or canceled

The reason for participant discontinuation or withdrawal from the study will be recorded on the Case Report Form (CRF). Subjects who sign the informed consent form and are randomized but do not receive the study intervention may be replaced. Subjects who sign the informed consent form, and are randomized and

receive the study intervention, and subsequently withdraw, or are discontinued from the study, will be replaced.

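### Do the forecasts of 32 and 14 evaluable youth and 44 eligible youth need correcting because the cited rates do not yield them?

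*Combined protocol and SAP*

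**What the plan says.** Section 5 (Study Population) plans 54 youth, 36 on CBT and 18 on CBT+CCT. It cites two parent-study rates, 96.2% for therapy retention and 89% for fMRI motion, and on that basis says "we expect to have 32 CBT-treated and 14 CBT+CCT-treated anxiety youth with usable pre- and post-treatment data". It gives one pair of rates for both arms and shows no steps.

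The same section says that the parent study "has successfully recruited and retained over 100 anxious youth", forecasts over 100 more randomized 2:1 by 05/31/2021, notes that nearly all RMT youth go on to CBT, and adds "thus we expect 44 youth to be eligible for the CBT+CCT". Section 4.1 gives the parent study's size: "210 youths (7-17 years) with impairing anxiety are being recruited and randomized 2:1".

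Three other provisions bear on losses:
- Section 7.2 says that youth who "receive the study intervention, and subsequently withdraw, or are discontinued from the study, will be replaced".
- Section 8.1.3 says that, when more than about six weeks have passed since the second parent-study scan, "a repeat scan may be obtained prior to the onset of CBT+CCT".
- Section 6.3 draws the CBT+CCT arm from all possible RMT participants in the parent study, and Section 5.1 requires active enrolment there.

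**The concern.** One sentence derives two counts from one pair of rates, so both arms should show the same yield. They do not: 32 of 36 is 88.9% and 14 of 18 is 77.8%. The figure of 32 looks like motion loss alone, with therapy retention left out, while 14 looks like motion loss charged twice or some other loss specific to that arm. Likewise, 44 eligible youth follows a forecast of further accrual that, at 2:1, would supply fewer than 44 to RMT.

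These are the plan's only figures for the evaluable sample and the recruitment pool. If they were materially wrong, the precision of the primary imaging comparison could be misjudged, as could the feasibility of filling the CBT+CCT arm within a year. An expected differential loss in the experimental arm of a non-randomized comparison would also be worth knowing about.

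**Working it through.** **Inputs.** Enrolment of 36 and 18, rates of 0.962 and 0.89, stated counts of 32 and 14 (total 46), and an eligible pool of 44 (all Section 5). Parent-study target of 210 at 2:1 (Section 4.1). Over 100 recruited and over 100 to come (Section 5).

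**Evaluable counts, both rates once.** Combined yield = 0.962 × 0.89 = 0.856.
- CBT: 36 × 0.856 = 30.8, against 32 stated (difference +1.2).
- CBT+CCT: 18 × 0.856 = 15.4, against 14 stated (difference −1.4).
- Total: 54 × 0.856 = 46.2, against 46 stated.

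Rounded, this is 31 and 15. The total is reproduced and the split is not.

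**Could one common yield give both counts?** Let the yield be y, applied to each arm total. Reaching 32 of 36, even by rounding up, needs y > 31/36 = 86.1%. Reaching 14 of 18, even by rounding down, needs y < 15/18 = 83.3%. The ranges do not overlap, so no common yield works under any rounding.

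**Could arm-specific losses give them?**
- CBT, motion loss only: 36 × 0.89 = 32.0. This is what replacement of withdrawals under Section 7.2 would produce.
- CBT+CCT, motion loss only: 18 × 0.89 = 16.0, which is not 14.
- CBT+CCT, motion twice: 18 × 0.89² = 14.3.
- CBT+CCT, retention once and motion twice: 18 × 0.962 × 0.89² = 13.7.
- CBT+CCT, retention twice and motion once: 18 × 0.962² × 0.89 = 14.8, or 14 rounded down.

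So 32 and 14 can each be reached, but only with different losses in the two arms. The protocol does not say that this was done.

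**Does the difference matter for precision?** The 80%-power detectable difference between groups in pre-to-post change, two-sided 0.05, in SD units, is approximately (1.960 + 0.842) × √(1/n₁ + 1/n₂).
- 32 and 14: 2.802 × √(1/32 + 1/14) = 0.90.
- 31 and 15: 2.802 × √(1/31 + 1/15) = 0.88.

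The noncentral t gives 0.92 and 0.90. Either way the two splits differ by about 0.02 SD. Section 9.3.1 sets different thresholds for fMRI data, so these values serve only to compare the two splits.

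**Eligible pool.** Remaining accrual is at most about 210 − 100 = 110. At 2:1, 100 to 110 further youth put 100/3 = 33.3 to 110/3 = 36.7 into RMT. A pool of 44 from new randomizations alone would need 44 × 3 = 132. The shortfall is 44 − 36.7 = 7.3 to 44 − 33.3 = 10.7 youth. The whole parent study supplies 210/3 = 70 to RMT, and the first 100 recruited would already have put about 33 there. If 7 to 11 of those were still in RMT or had yet to start their optional CBT, the pool would be 44. The documents do not give that number.

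**The case for a change.** The strongest argument for a change is that the split is shown to be inconsistent from the protocol's own numbers, without guessing the sponsor's rule. With no power analysis, Section 5 is the only place to judge how precise the pilot's effect sizes will be, and a correction would cost a line of text. The arithmetic part of this stands: the two rates do not give 32 and 14 under any common application, and the working is not shown.

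The rest carries less weight. The arms do not share a path. CBT+CCT youth come through a full RMT course before CBT and may have a repeat scan before treatment, while CBT youth have one course and the parent study's two scans. A heavier loss in CBT+CCT is natural, and the provisions that would cause it are in the protocol; only their use in the forecast is unstated.

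For the 44, Sections 5.1 and 6.3 do not limit the pool to youth still to be randomized, and both accrual figures are open-ended (over 100). Putting 33 to 37 in its place could insert a figure with less support than the one removed.

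Section 4.1 also allows that "at P.I. discretion, participants may not be required to complete an fMRI", so the imaging count actually obtained may differ from any forecast. That is a separate question of data completeness and does not bear on this arithmetic.

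**Conclusion.** The split of 32 and 14 does not follow from the two cited rates applied alike to both arms; 31 and 15 does. This is either a small slip or an arm-specific allowance that was not written down. It amounts to 1.2 and 1.4 youth in opposite directions, with the total still 46. The 44 is unexplained but not shown to be wrong: it needs about 7 to 11 youth already in RMT, which is an assumption the documents neither state nor exclude.

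Nothing rests on these figures. Section 9.2 says no power analysis was possible. The repeated-measures ANOVAs of Sections 9.3.2 and 9.3.3 will use whatever data are obtained. Even the lowest reading of the pool, 33, is well above the 18 needed. Writing out the attrition steps would record a derivation without altering who is enrolled, what is measured, how it is analysed or what the pilot can conclude. No change to the plan is called for.
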